### 10.1.2. Sample Size Re-estimation

Due to the slower than anticipated rate of study recruitment, during recruitment to cohort 3 of the study, a review of the standard deviation of daily change from baseline in  $\log_{10}(\text{CFU})$  was performed to assess if the initial estimate of the standard deviation (0.2) was comparable to the observed study data available at that time. The review included CFU data from participants in the first 2 cohorts and included only participants who completed assessments from baseline through to Day 14. The average daily change from baseline was calculated as change between baseline and Day 14 divided by 14, then the standard deviation summarised by treatment group. The results are displayed in the following table.

Treatment Group	N	Daily Change from Baseline in $\log_{10}(\text{CFU})$ Standard Deviation
Standard-of-care	9	0.049
GSK3036656 5mg	15	0.067
GSK3036656 15mg	13	0.053

The observed standard deviations were smaller than used in the original sample size simulation therefore the sample size simulations described in Section 10.1 were repeated using standard deviations of 0.1 and 0.15 and including additional sample sizes of 9 and 12 participants per treatment arm. The results for the percentage of studies showing a mean change from baseline below zero, assuming a standard deviation of 0.15, is shown in the following figure.

Assuming a standard deviation of 0.15, a sample size of 9 participants per treatment arm would provide approximately the same level of confidence as originally planned assuming a standard deviation of 0.2 and a sample size of 15 participants per treatment arm i.e. Assuming a true underlying change from baseline of -0.06 and a sample size of 9 participants per treatment arm, there is approximately 90% chance of the observed mean change being a negative value (i.e. a positive response). Therefore, this supports reducing the sample size in ongoing and future cohorts to 9 participants per GSK3036656 treatment arm.

## 10.2. Populations for Analyses

For purposes of analysis, the following populations are defined:

Population	Description
Screened	All participants who were screened for eligibility.
Enrolled	All participants who passed screening and entered the study.
Randomised	All participants who were randomly assigned to treatment in the study.
Pharmacokinetic (PK)	Participants in the safety population who received at least one dose of GSK3036656 and have at least one evaluable PK sample. Participants will be analysed according to the treatment actually received.
Efficacy	Participants in the safety population who provided at least two evaluable overnight sputum sample.
Safety	All randomized participants who received at least 1 dose of study treatment. Participants will be analysed according to the treatment they actually received.

Data from the standard of care arm will be pooled for the final analysis.

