## 5.5. Scientific Rationale for Study Design

EBA studies are currently the only available way of assessing drug activity against TB early in drug development. EBA is a surrogate efficacy endpoint (decline of sputum bacterial counts) which allows the estimation of early drug effects in studies that are significantly shorter than studies using definitive clinical endpoints (e.g., relapse-free cure). CCI

EBA has a number of well-recognised limitations [Burman, 2003], and alternative surrogate endpoints are urgently needed. Studies evaluating the Mtb response to therapy in DS-TB subjects by CCI have already been reported, though at later timepoints, and a further study reporting the day 14 response has recently completed recruitment. CCI

Dose ranging is necessary to investigate the relationship between dose/exposure and efficacy, and to select an optimal dose for further progression into the clinic. Due to findings of cardiovascular toxicity in dogs, it is recommended that systemic exposures to GSK3036656 in humans do not exceed certain predefined limits (see Section 5.6). The PK of GSK3036656 has only been studied in healthy volunteers and its PK in TB participants is unknown. Therefore, to minimize the risk of exceeding the predefined exposure limits, a dose escalation approach will be used where the starting dose in the study is lower than doses previously administered safely to healthy volunteers with subsequent selection of doses based on PK and safety results.

The Rifafour e-275 (or equivalent generic alternative) treatment group is included as a benchmark for the EBA quantitative mycobacteriology and to evaluate whether HRZE in this population gives similar EBA results to that demonstrated in prior studies with this combination. A negative control arm, where subjects are left untreated, would be unethical due to the availability of effective treatment and the consequences of not treating TB.

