## 10.3. Statistical Analyses

### 10.3.1. Activity/Pharmacokinetic Analyses

Endpoint	Statistical Analysis Methods
Primary	Rate of change in log 10 CFU per mL direct respiratory sputum samples over the period baseline to Day 14 (EBA CFU 0-14 ). This will be analysed using a mixed effects model including treatment, day, BMI and treatment-by-day as covariates.  This endpoint will be analysed using the efficacy population.
Secondary	PK Endpoints  Pharmacokinetic analysis will be the responsibility of the Clinical Pharmacology Modeling and Simulation Department, (CPMS), GlaxoSmithKline. Plasma GSK3036656 concentration-time data will be analyzed by non-compartmental methods with WinNonlin 5.2 or higher.

Endpoint	Statistical Analysis Methods

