The primary endpoint may be analysed once data is available for 12 evaluable subjects, as per the sample size re-estimation calculations, on the second consecutive cohort that reaches or exceeds the target PK plasma exposure for efficacy (based on the murine infection model), and subsequent cohorts. The purpose of this efficacy analysis is to optimise dosing for subsequent cohorts (e.g. to help estimate the dose response curve) as well as to aid internal decision making.

The DEC is empowered to take the following decisions for subsequent cohorts:

- To select a higher dose (including a loading dose that may be given over 1 or more days) within the limits defined in Section 5.6.
- To select a dose lower than, or the same as, a preceding dose.
- To stop dosing.
- To include additional pharmacokinetic assessments.
- To include additional timepoints for an existing safety assessment.
- To adjust the haemoglobin exclusion and stopping criteria if no haematological abnormalities are observed in the review of safety data from the highest dose cohort (Cohort 3). For the subsequent cohort(s) receiving a lower dose of GSK3036656, the haemoglobin exclusion criterion will be lowered to <8.0 g/dL, and the haemoglobin stopping criterion will be lowered to <6.0 g/dL. Patients with a confirmed haemoglobin <8.0g/dL after randomisation will require enhanced observations, with a repeat haemoglobin level and discussion of patient status with the GSK medical monitor.

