## **6. STUDY POPULATION ANALYSES**

### **6.1. Overview of Planned Study Population Analyses**

The study population analyses will be based on the Safety population, unless otherwise specified.

Study population analyses including analyses of participant's disposition, protocol deviations, demographic and baseline characteristics, prior and concomitant medications, and exposure will be based on GSK Core Data Standards. Details of the planned displays are presented in [Appendix 10: List of Data Displays](#).

Data from the standard of care arm will be pooled for the analysis, except for the display of Summary of Participant Disposition at Each Study Epoch, which will be displayed by cohort.

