**7.1.5.1. Statistical Methodology Specification**

Endpoint

 
• Rate of change in log10CFU per ml direct respiratory sputum samples over the period baseline to Day 14.
 

Model Specification

Model 1:
 
 
• Mixed model repeated measures analysis. Terms in the model:             
 
• Response: log10CFU
 
• Categorical: treatment
 
• Continuous: time, BMI
 
• Interaction: treatment*time
 
• Random: Subject
 
 
 
 
Model 2:
 
In addition, to characterize any bi-linear characteristics a bi- linear Bayesian regression model of the following form will also be fitted:
 $y_i = \begin{cases} \text{normal}(\alpha + \beta_1(t_i - cp), \sigma^2) & \text{if } t_i < cp \\ \text{normal}(\alpha + \beta_2(t_i - cp), \sigma^2) & \text{if } t_i \geq cp \end{cases}$ 
 
• Where cp=change (node) point as determined by the data (separate nodes for each treatment group), and t=time.
 
• The model will include terms for intercept, BMI, treatment, treatment*day before node, treatment*day after node, subject.
 
• This model would utilize uninformative uniform priors for cp and <math>\sigma^2</math> (discrete uniform(2,13) and uniform(0,5) respectively) and uninformative normal priors for the intercept, treatment, baseline log10CFU and BMI (normal(0,var=1000000)). Subject will be a random effect with an uninformative prior (normal(0,var), where var=uniform(0,5)).
 
• The efficacy population will be used for both models.
 
• Data from the standard of care arm will be pooled for the analysis.
 
• Where CFU plate counts are Too Numerous To Count (TNTC) a value of 2500 should be imputed for both models.
 

Model Checking & Diagnostics

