## 12.10.7. Safety Tables

Safety: Tables					
No.	Population	IDSL / Example Shell	Title	Programming Notes	Deliverable
Adverse Events (AEs)					
3.1.	Safety	AE5B	Summary of All Adverse Events by System Organ Class, Preferred Term and Maximum Grade	ICH E3	SAC
3.2.	Safety	AE5B	Summary of All Drug-Related Adverse Events by System Organ Class, Preferred Term and Maximum Grade	ICH E3	SAC
3.3.	Safety	AE15	Summary of Common (>=5%) Non-serious Adverse Events by System Organ Class and Preferred Term (Number of Subjects and Occurrences)	FDAAA, EudraCT	SAC
Serious and Other Significant Adverse Events					
3.4.	Safety	AE16	Summary of Serious Adverse Events by System Organ Class and Preferred Term (Number of Subjects and Occurrences)	FDAAA, EudraCT	SAC
3.5.	Safety	AE5B	Summary of Adverse Events Leading to Permanent Discontinuation of Study Treatment by System Organ Class, Preferred Term and Maximum Grade	IDSL	SAC
3.6.	Safety	AE5B	Summary of Adverse Events Leading to Withdrawal from Study by System Organ Class, Preferred Term and Maximum Grade	IDSL	SAC
3.7.	Safety	AE20	Summary of Serious Fatal and Non-Fatal Drug-Related Adverse Events by Overall Frequency	Plain Language Summary requirements (PLS).	SAC
3.8.	Safety	PAN10	Summary of Exposure Adjusted Incidence Rates of Adverse Events Over Time Relative to COVID-19 Pandemic Measures		SAC
3.9.	Safety	PAN10	Summary of Exposure Adjusted Incidence Rates of Adverse Events Over Time By Age Relative to COVID-19 Pandemic Measures		SAC

Safety: Tables					
No.	Population	IDSL / Example Shell	Title	Programming Notes	Deliverable
Laboratory: Chemistry					
3.10.	Safety	LB1	Summary of Chemistry Changes from Baseline	ICH E3	SAC
3.11.	Safety	LB17	Summary of Worst Case Chemistry Results by PCI Criteria Post-Baseline Relative to Baseline	ICH E3	SAC
Laboratory: Haematology					
3.12.	Safety	LB1	Summary of Haematology Changes from Baseline	ICH E3	SAC
3.13.	Safety	LB17	Summary of Worst Case Haematology by PCI Criteria Post-Baseline Relative to Baseline	ICH E3	SAC
Laboratory: Urinalysis					
3.14.	Safety	UR1	Summary of Worst Case Urinalysis Results Post-Baseline Relative to Baseline	ICH E3	SAC
Laboratory: Hepatobiliary (Liver)					
3.15.	Safety	LIVER1	Summary of Liver Monitoring/Stopping Event Reporting	IDSL	SAC
3.16.	Safety	LIVER10	Summary of Hepatobiliary Laboratory Abnormalities	IDSL	SAC
ECG					

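### If the haemoglobin criteria are relaxed for a later lower-dose cohort, pooled standard of care is a mismatched reference for the absolute haemoglobin flag; show it split by criterion as well

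*Protocol*

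**What the plan says.** **Pooling.** Protocol 10.2: "Data from the standard of care arm will be pooled for the final analysis". SAP 5.1 has a single Rifafour display group for all cohorts. SAP 6.1 repeats the rule for study population displays and makes one exception: "pooled for the analysis, except for the display of Summary of Participant Disposition at Each Study Epoch". SAP 7.1.5.1 applies pooling to both primary efficacy models. SAP 8 (safety) provides no SoC display by cohort, so haematology follows the single group of SAP 5.1.

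**Entry and stopping limits.** Protocol 6.2 excludes haemoglobin below 10.0 g/dL, and Protocol 8.1.3 stops treatment below 8.0 g/dL. Both may be adjusted under Protocol 11. If Cohort 3 shows no haematological abnormality, then for later cohorts on a lower dose "the haemoglobin exclusion criterion will be lowered to <8.0 g/dL" and the stopping limit becomes 6.0 g/dL.

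**Displays.** SAP Table 3.12 gives haematology change from baseline. Table 3.13 is the "Summary of Worst Case Haematology by PCI Criteria Post-Baseline Relative to Baseline". The criteria of potential clinical importance (SAP 12.8.1) flag haemoglobin below 75 g/L and, separately, a decrease of 25 g/L. Neither varies by cohort.

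**Role of SoC.** Protocol 5.5: "The Rifafour e-275 (or equivalent generic alternative) treatment group is included as a benchmark for the EBA quantitative mycobacteriology". Protocol 10.1.1 rules out formal comparisons of GSK3036656 with SoC.

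**The concern.** Each cohort randomises its own SoC participants 3:1. Within a cohort, the two arms share the same entry and stopping limits. Pooling SoC over cohorts gives up that match if the limits change part-way.

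An absolute flag depends on where a participant starts. A column drawn wholly from people who could enter at 80 g/L would stand beside a column drawn mostly from people who had to enter at 100 g/L or more. Calling the flag relative to baseline does not remove this: someone entering at 82 g/L is unflagged at baseline, and a fall of just over 7 g/L makes a new flag.

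Protocol 3.3.1 names reduction in red cells as a risk, and the safety evidence here is descriptive. A contrast produced by eligibility alone should be recognisable in the table.

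**Working it through.** The plan gives no figure on this point to reproduce.

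**1. Share of pooled SoC under the new criteria.** Protocol 5.1 gives 3-5 SoC participants per cohort. Assume 5 + 5 in Cohorts 1-2, 3 in Cohort 3 and 3 in each later cohort.
- Only Cohort 4 under the new criteria: w = 3/(13 + 3) = 3/16 = 19% (3/18 = 17% if Cohort 3 has 5).
- Cohorts 4 and 5: w = 6/(13 + 6) = 6/19 = 32%.
- The later GSK3036656 arm: 9/9 = 100%.

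**2. Distances on the haemoglobin scale.**

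| | Original | Adjusted |
|---|---|---|
| Lowest eligible entry | 100 g/L | 80 g/L |
| Fall needed to reach the 75 g/L flag | 25 g/L | 5 g/L |
| Stopping limit | 80 g/L | 60 g/L |
| Stopping limit minus flag | +5 g/L | -15 g/L |
| Lowest entry minus stopping limit | 20 g/L | 20 g/L |

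Under the original limits stopping comes before the flag; under the adjusted limits the flag comes first.

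**3. Ratio of flag rates with no drug effect.** Let p_old and p_new be the flag rates under the two criteria. Pooled SoC expects p_pool = (1 - w) p_old + w p_new. As p_old approaches zero, p_new/p_pool approaches 1/w: 16/3 = 5.3 or 19/6 = 3.2. This limit depends only on arm sizes.

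**4. Size of p_new.** The documents give no entry distribution, so two sets of assumptions were tried.

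*Set A.* Entry haemoglobin x uniform from a floor to 130 g/L, mean fall 3 g/L, visit SD 6 or 8 g/L, and 9 independent post-baseline values (Days 2-7, 8, 14 and 28 in the Schedule of Activities). P(flag | x) = 1 - [1 - Φ((75 - (x - 3))/SD)]^9, averaged over x.

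| Entry floor | p (SD 6; SD 8) | Ratio to pooled, w = 3/16 | Ratio to pooled, w = 6/19 |
|---|---|---|---|
| 100 g/L (original) | 0.005%; 0.2% | - | - |
| 95 g/L | 0.1%; 1.2% | 4.4; 3.0 | 2.9; 2.3 |
| 90 g/L | 1.1%; 4.6% | 5.2; 4.4 | 3.1; 2.9 |
| 80 g/L | 14%; 20% | 5.3; 5.1 | 3.2; 3.1 |

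*Set B.* Entry haemoglobin normal (mean 105-125, SD 15 g/L) truncated at the limit, visit SD 4-7 g/L, 5 post-baseline values, common change -1.5 to -5 g/L, w = 3/16. The range of change follows the first-in-human means in Protocol 3.3.1 (-1.5 and -4.9 g/L).
- New value below 75 g/L: 0.1-8.4% in the new cohort against 0.02-2.3% in pooled SoC, for example 1.55/0.29 = 5.3 and 2.85/0.80 = 3.6.
- Chance of at least one flag among 9: 0.8-54%, against 0.1-19% at the pooled SoC rate.
- Mean change from baseline: old and new criteria within 0.05 g/L.
- Decrease of 25 g/L: 8.1% against 8.1% in the scenarios where it is most frequent.
- Any single value below the stopping limit: at most 0.4% under the adjusted rule against 3.2% under the original. Protocol 8.1.3 normally asks for confirmation on two samples, so real rates would be lower. The direction is opposite to the flag.

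**5. Early bactericidal activity (EBA).** The model is a "mixed effects model including treatment, day, BMI and treatment-by-day as covariates", with no cohort term. With the observed SoC SD of 0.049 per day (Protocol 10.1.2), the SE of a cohort's SoC mean is 0.049/√5 = 0.022 to 0.049/√3 = 0.028. Between 13 earlier and 3 later SoC participants the SE of a difference is 0.049 × √(1/13 + 1/3) = 0.031, so 80% power needs a drift of about 2.8 × 0.031 = 0.088 per day.

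**The case against.** The case against acting is substantial, and much of it stands.

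- **The change may never happen.** It is optional and requires a clean Cohort 3. This stands, so the fix should be conditional.
- **The named risk is a reduction, and reductions are shown properly.** Table 3.12 and the 25 g/L decrease flag compare each participant with himself, and step 4 shows that neither moves. This stands. What remains is the absolute row of Table 3.13, plus discontinuations driven by haemoglobin (Tables 1.3 and 3.5), which follow different limits.
- **Individual data are displayed.** Figure 3.4 plots each participant's profile, and Listing 22 gives all haematology for anyone flagged. A careful reader could see that a flag began near 80 g/L. That helps with individual cases, but it does not show which SoC participants are the right denominator.
- **Nothing formal depends on the pooled column.** No formal SoC comparison is planned, and the escalation rule in Protocol 8.2 refers to the SoC subgroup when judging the last dose level. This stands.
- **The rate could be trivial.** The Amendment 5 rationale describes screen failures as only slightly under the limit, which favours the 90-95 g/L floors: 9 × 0.1% = 0.01 to 9 × 4.6% = 0.4 expected flags in an arm of 9. This limits the size, not the direction.

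A reader might also infer that pooling hides drift in the EBA benchmark. The documents do not support that. The SoC arm is there to check the assay against prior studies of the same combination, each arm's own slope is reported, and Figure 2.3 and Listing 36 retain SoC data by participant, with dates in the listing. Amendment 4 permits a generic product; it does not say that a switch occurred.

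**Conclusion.** The point holds as a limited one about descriptive reporting. If the DEC relaxes the haemoglobin limits, the absolute row of Table 3.13 will set a GSK3036656 arm enrolled wholly under the new limits beside an SoC column that is 68-81% (13/19 to 13/16) original-criterion. With no drug effect, the flag can be about 2 to 5 times as frequent in that arm. The direction follows from the cut-offs, and the ratio mainly from arm sizes. The absolute rate, from about 0.1% to 20% across the scenarios, rests on assumed entry haemoglobin and visit variation and should not be quoted as an expected result.

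It would be tempting to conclude that the lowest dose will look haematotoxic. The documents do not establish which dose is affected: SAP 5.1 lists 5, 15 and 30 mg and leaves Doses 4 and 5 open, and the 5 mg arm preceded the change. Nor is haemoglobin reporting as a whole compromised, since change from baseline and the decrease flag are essentially unaffected.

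**What to change.** Keep the pooled Rifafour column. Add to the SAP that, if the DEC adjusts the haemoglobin criteria, Table 3.13, Figure 3.4 and Listings 22-23 will also show Rifafour split by the criterion in force at enrolment (original or adjusted). Each GSK3036656 arm's absolute haemoglobin flags should be read against the matching SoC group. A footnote to Tables 1.3 and 3.5 should say that the haemoglobin stopping limit differed between cohorts.

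Optionally, add descriptive SoC rows by cohort to Tables 2.1-2.3 as an assay check. State there that with 3-5 SoC participants per cohort (SE about 0.022-0.028 per day) only a large drift would be visible.

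The cost is a few lines of SAP text and some extra columns or rows; no new data are needed and the pooled estimates do not change. The drawback is group size: about 13-15 SoC participants under the original criterion and 3-6 under the adjusted one. The split can only be descriptive and should be labelled so.

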## 10.3. Statistical Analyses

### 10.3.1. Activity/Pharmacokinetic Analyses

Endpoint	Statistical Analysis Methods
Primary	Rate of change in log 10 CFU per mL direct respiratory sputum samples over the period baseline to Day 14 (EBA CFU 0-14 ). This will be analysed using a mixed effects model including treatment, day, BMI and treatment-by-day as covariates.  This endpoint will be analysed using the efficacy population.
Secondary	PK Endpoints  Pharmacokinetic analysis will be the responsibility of the Clinical Pharmacology Modeling and Simulation Department, (CPMS), GlaxoSmithKline. Plasma GSK3036656 concentration-time data will be analyzed by non-compartmental methods with WinNonlin 5.2 or higher.

Endpoint	Statistical Analysis Methods
	
Calculations will be based on the actual sampling times recorded during the study.
 
From the plasma concentration-time data, the following pharmacokinetic parameters will be determined, as data permit:
 
 
• maximum observed blood concentration (Cmax)
 
• time to Cmax (tmax)
 
• area under the plasma concentration-time curve [AUC0-t and AUC0-24]
 
• trough concentration (Cτ).
 
 
AUC0-t or AUC0-24 and Cmax may be used for assessment of dose proportionality. Trough concentration (Cτ) samples collected on the specified days will be used to assess attainment of steady state.
 
Pharmacokinetic data will be presented in graphical and/or tabular form and will be summarized descriptively.
 
Statistical analyses of the pharmacokinetic parameter data will be the responsibility of Statistics, Programming and Data Strategy (SPDS), GlaxoSmithKline. Distributional assumptions underlying the statistical analyses will be assessed by visual inspection of residual plots. Normality will be examined by normal probability plots, while homogeneity of variance will be assessed by plotting the residuals against the predicted values for the model. Alternative analyses of the data will be performed if any of the model assumptions appear to be violated. Full details on the statistical aspects will be detailed in the Reporting and Analysis Plan (RAP).
 
Dose Proportionality
 
Dose proportionality will be assessed via analyses of AUC0-t or AUC0-24 and Cmax. A statistical analysis will be performed using the power model. The analysis will be performed on loge-transformed data. For each of these parameters a mixed effects model will be fitted with loge (dose) as a fixed effect and individual subject fitted as random effects. Estimates of the mean slopes of loge (dose) will be reported along with corresponding 90% confidence intervals (slope≈1 implies dose proportionality).
 
Achievement of Steady State
 
Trough concentration levels, Cτ, collected pre-morning dose will be plotted by collection day and dose. To evaluate whether steady state was achieved, statistical analysis of Cτ will be performed after a log-transformation of the dose data. A mixed effect model will be fitted with dose, day and dose-by-day interaction as fixed effects (with dose as a factor and day as a continuous covariate) and subject as a random effect. The coefficients of the


Endpoint	Statistical Analysis Methods
	
slopes for the day effect for each dose, along with corresponding 90% confidence intervals, will be used to determine whether steady state was achieved.
 
Efficacy/Activity Endpoints
 
EBA CFU0-2, EBA CFU2-14, EBA TTP0-14, EBA TTP0-2 and EBA TTP2-14 will be analysed similarly to the primary endpoint. These endpoints will be analysed using the efficacy population.

Exploratory	Will be analysed and reported separately.

